We anticipate enrolling approximately 55 patients as we anticipate an approximate 10% attrition rate in order to have study outcomes for 50 subjects in total. However, the attrition rate for a study of this length is unclear and we may need to enroll a different number of subjects to achieve our analyzable population of 50 subjects.

d) Study-Wide Number of Subjects*

If this is a multicenter study, indicate the total number of subjects to be accrued across all sites.

This is the only enrollment site.

e) Study Timelines*

Describe:

- *The duration of an individual subject's participation in the study.*

Approximately 12 weeks of in person follow up visits, with a final phone call three months after completion of antibiotic treatment. Thus, the total duration of an individual subject will range from 16 weeks to 24 weeks.

- *The duration anticipated to enroll all study subjects.*

Approximately 16 months.

- *The estimated date for the investigators to complete this study (complete primary analyses)*

Approximately 2 years.

f) Study Endpoints*

Describe the primary and secondary study endpoints. Describe any primary or secondary safety endpoints.

PROTOCOL TITLE: *Tolerability, Safety, and Efficacy of Tedizolid as Oral Treatment for Bone and Joint Infection*

Revised: 8/10/18 Version 1.6

The primary study endpoint is the tolerability of prolonged (≥ 4 weeks) courses of tedizolid antibiotic therapy for patients with bone and joint infection. CBC and a CMP (comprehensive chemistry panel including liver function tests) will be performed at the following intervals after initiation of tedizolid. We will administer standardized surveys about drug side effects and tolerability at all follow-up visits (weeks 1, 2, 3, 4, 5, 6 (optional), 7 (optional), 8 (optional), 9 (optional), 10 (optional), 11 (optional), 12). Adverse events will be measured using the Medical Dictionary for Regulatory Activities Terminology (MedDRA) version 18.1 (or the most current version).

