The secondary study endpoint is the safety of prolonged (≥ 4 weeks) courses of tedizolid antibiotic therapy for patients with bone and joint infection. CBC and a CMP (comprehensive chemistry panel including liver function tests) will be performed at the following intervals after initiation of tedizolid. We will administer standardized surveys about drug side effects at all follow visits (weeks 1, 2, 3, 4, 5, 6 (optional), 7 (optional), 8 (optional), 9 (optional), 10 (optional), 11 (optional), 12). Adverse events will be measured using the Medical Dictionary for Regulatory Activities Terminology (MedDRA) version 18.1 (or the most current version).

The tertiary study endpoint is efficacy, which will be defined using criteria as determined by the subject's primary provider. Specifically, cure will be defined as no need for further antibiotics beyond the originally planned duration (i.e., 6 weeks for non-device associated bone and joint infection or until hardware removal for subjects with implants). Unplanned surgical procedures prompted by inadequate infection control will be categorized as treatment failure. We will also measure long-term efficacy by performing a phone survey 3 months after completion of antibiotics. Recurrence of signs or symptoms of bone and joint infection will be considered a long-term treatment failure. Confirmation of subjects self-report with medical record review will be performed on an as needed basis when categorization of self-reported outcomes is not clear.

g) Procedures Involved in the Human Research*

Describe and explain the study design.

The design of this study is a prospective, open-label, non-comparative clinical trial of tedizolid for the treatment of bone and joint infection. We will follow patients for between 16 and 24 weeks, depending on the length of their antibiotic treatment, for the purpose of determining tolerability, safety, and efficacy of prolonged use (≥ 4 weeks) of tedizolid in the treatment of bone and joint infection. Participants will be enrolled regardless of race, ethnicity, or gender (as long as they are within 18-85 years of age).

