Subjects will be given tedizolid orally 200 mg once daily for duration of therapy of between 4 and 12 weeks. The exact duration of tedizolid therapy will be decided by the subject's treating physician. In other words, the primary/consulting physician who is managing the treatment of the patient's bone and joint infection will be the one who decides the length of the tedizolid treatment.

Safety and tolerability of tedizolid through this study will be guaranteed for 12 weeks. Provision of tedizolid therapy beyond 12 weeks is not guaranteed by the clinical trial as excessively prolonged therapy is associated with increased monitoring cost (e.g., subject payments, laboratory tests, clinic utilization costs). If patients require greater than 12 weeks of therapy for Gram-positive pathogens, study

PROTOCOL TITLE: *Tolerability, Safety, and Efficacy of Tedizolid as Oral Treatment for Bone and Joint Infection*

Revised: 8/10/18 Version 1.6

staff will contact the subject's primary provider to arrange alternative oral or IV therapy. Medications will be provided by the Investigational Drug Service (IDS) on the LA BioMed/Harbor-UCLA campus, which supplies all research related medications to study subjects at our center.

Subjects will be enrolled as outpatients or as inpatients when discharge is expected in the near future (\leq 1 week). [name], the primary investigator, and his team will advise the hospital staff of the study and seek their assistance in identifying and notifying the study staff of possible subjects who have presented to the Emergency Department, Inpatient Floors, or Outpatient Clinic with bone and joint infection. The Investigator or study staff will approach the subject's primary treatment team and ask for their permission to introduce the study and the study staff to the patient. Study staff will then present information about the study (See Recruitment Script V1.0) to see if they are interested. Permission will be sought from the subject by their primary treatment team before anyone outside the patient's primary treating team approaches them about the study.

Once an interested patient is identified, study staff will explain the details of the study to the subject. If the patient is interested in participating, study staff will complete the informed consent process in a private setting in the patient's preferred language (English or Spanish).

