The subjects will be paid in cash for their follow up visits. They will be paid \$30 for the visit on week 1, \$35 for the visit on week 2, \$40 for the visit on week 3, \$40 for the visit on week 4, \$45 for the visit on week 5, \$45 for the visit on week 6, and \$50 each visit for visits on weeks 7, 8, 9, 10, 11, 12 and 13.

The total amount of compensation will range between \$240 and \$585 based on the number of follow up visits the subject completes. All subjects will complete visits on Weeks 1,2,3,4,5, and 12. Subjects still taking the study drug at week 6 will be required to return for a Week 6 follow up visit. Subjects still taking the study drug at week 7 will be required to return for a week 7 follow up visit, and so on- while patients are receiving the study drug they will return for weekly follow up visits until they have completed the course, or until they have reached 12 weeks. Once subjects complete the course of the study drug, they will return for one additional weekly follow up visit (e.g. if a patient completes the study drug at 7 weeks, they will return for visits on weeks 1-8 and week 12). If subjects take the study drug for 12 weeks, they will return for a final follow up visit on week 13.

A phone survey 3 months after the subject's completion of antibiotics will be performed. They will be asked about their overall well-being, recurrence of signs or symptoms of bone and joint infection and any self-reported medical conditions or adverse events (medical record review will be performed on an as needed basis when categorization of self-reported outcomes is not clear).

Provide a description of all procedures being performed and when they are performed, including procedures being performed to monitor subjects for safety or minimize risks. Include procedures

PROTOCOL TITLE: *Tolerability, Safety, and Efficacy of Tedizolid as Oral Treatment for Bone and Joint Infection*

Revised: 8/10/18 Version 1.6

being performed already for diagnostic or treatment purposes and differentiate between these and the procedures performed solely for the research.

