Additionally, subjects may be withdrawn in the following circumstances development of significant cytopenias and liver function abnormalities, symptoms of neuropathy, gastrointestinal intolerance, or, in the opinion of the investigator, any new severe signs or symptoms that may be related to the study drug.

PROTOCOL TITLE: *Tolerability, Safety, and Efficacy of Tedizolid as Oral Treatment for Bone and Joint Infection*

Revised: 8/10/18 Version 1.6

If a subject becomes pregnant during the study, they will be discontinued from the study drug. Study staff will follow and collect data on the course of the pregnancy and the health of the child for at least 6-8 weeks after delivery.

Describe any procedures for orderly termination.

Termination of the study will occur based on the primary investigators judgment. Subjects will be provided referrals for their medical conditions, if needed.

Describe procedures that will be followed when subjects withdraw from the research, including partial withdrawal from procedures with continued data collection.

Subjects who withdraw from the study will be asked to notify the study team. No further visits will be required. Additionally, if a subject withdraws from the study, a member of the study team will contact their primary treatment physician and/or infectious disease consultant to ensure that the patient is given antibiotic therapy immediately upon discontinuation of study drug.

10) Risks to Subjects*

List the reasonably foreseeable risks, discomforts, hazards, or inconveniences to the subjects related the subjects' participation in the research. Include as may be useful for the HSC's consideration, describe the probability, magnitude, duration, and reversibility of the risks. Consider physical, psychological, social, legal, and economic risks.

According to the package insert for tedizolid (Sivextro), adverse reactions were evaluated for 1050 patients treated with tedizolid (200 mg oral/intravenous once daily for 6 days) in two Phase 2 and two Phase 3 ABSSSI (acute bacterial skin and soft structure infection) clinical trials. The median age of patients treated with tedizolid (200 mg oral/intravenous once daily for 6 days) in the Phase 2 and Phase 3 ABSSSI trials was 42 years, ranging between 17 and 86 years old. Patients treated with tedizolid (200 mg oral/intravenous once daily for 6 days) were predominantly male (65%) and white (82%).

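### The 3-month long-term efficacy call has no defined start for subjects who take another antibiotic after tedizolid, and symptom-free subjects in that group can count as long-term successes of tedizolid

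*Combined protocol and SAP*

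**What the plan says.** Section 9(e), Study Timelines, sets about 12 weeks of visits "with a final phone call three months after completion of antibiotic treatment" and concludes: "Thus, the total duration of an individual subject will range from 16 weeks to 24 weeks". Section 9(f), Study Endpoints, says "We will also measure long-term efficacy by performing a phone survey 3 months after completion of antibiotics", and its rule for that outcome is "Recurrence of signs or symptoms of bone and joint infection will be considered a long-term treatment failure". Section 9(g), Procedures, repeats the timing ("A phone survey 3 months after the subject's completion of antibiotics will be performed") and ties total follow-up to treatment length: "We will follow patients for between 16 and 24 weeks, depending on the length of their antibiotic treatment". Section 9(k), on safety monitoring, also times the call from the end of antibiotic treatment. None of these places names the last tedizolid dose.

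Three places allow antibiotics to outlast or replace tedizolid:

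- Section 9(g) limits tedizolid to 4 to 12 weeks. If a subject needs Gram-positive therapy for longer, "staff will contact the subject's primary provider to arrange alternative oral or IV therapy".
- Section 9(l), Withdrawal of Subjects, has the team make sure that a withdrawn "patient is given antibiotic therapy immediately upon discontinuation of study drug". It asks for no further visits and does not mention the call.
- Section 9(f) lets the originally planned course for subjects with implants run until the hardware is taken out, with no upper limit.

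Section 9(f) also has an earlier efficacy rule. Cure means no antibiotics beyond the originally planned duration, and unplanned surgery for poor infection control is failure. The plan does not say how this rule combines with the long-term one.

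**The concern.** The participation range treats the end of tedizolid and the end of antibiotics as the same date. For most subjects they may be. For a subject who moves to another Gram-positive drug they are not, and the plan does not say from which date the three months run, whether the call is made, or how the answer counts.

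The long-term outcome is meant to describe tedizolid. If the only failure criterion is recurrence of signs or symptoms, a second drug that suppresses or clears the infection yields a result that looks like tedizolid success. Subjects who need longer or different therapy are plausibly the harder cases. Section 9(i), Data Management, promises confidence intervals for efficacy and says that 50 subjects should reassure clinicians about efficacy as well as safety, so a reader will take the long-term rate at face value.

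**Working it through.** **Inputs.** Tedizolid for 4 to 12 weeks (9(g)); call 3 months after antibiotics end (9(e), 9(f), 9(g), 9(k)); participation of 16 to 24 weeks (9(e), 9(g)); 50 analyzable subjects (9(c)); anticipated cure rate 80% (9(i)).

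**1. The stated range.** Call week = T + 3 months, where T is total weeks of antibiotic.

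- With 3 months taken as 12 weeks: 4 + 12 = 16 and 12 + 12 = 24. This matches the protocol exactly.
- With 3 months taken as 13 weeks: 17 and 25.

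So the range takes T from the tedizolid window and has no room for T above 12.

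**2. Who falls outside, if the clock starts at the last antibiotic.** The call is by week 24 only if T ≤ 24 − 12 = 12 (or 24 − 13 = 11 with 13-week months).

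| T (weeks) | Call week (T + 12) |
|---|---|
| 6 | 18 |
| 12 | 24 |
| 14 | 26 |
| 18 | 30 |
| 24 | 36 |
| open-ended | never due |

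A subject who switches at week s can take 12 − s further weeks and still be called by week 24: 10 weeks if s = 2, 8 if s = 4, none if s = 12. A switch at week 2 within a 6-week course gives a call at week 18. Early switchers can therefore stay inside the range.

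**3. How a symptom-free switched subject is classified.**

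| Clock starts at | State at the call | Result under the long-term rule in 9(f) |
|---|---|---|
| Last tedizolid dose | May still be on, or recently off, the other drug | Not a failure |
| Last antibiotic, finite course | Off all antibiotics, but treatment was finished by the other drug | Not a failure |
| Last antibiotic, open-ended course | No call falls due | No result |

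Where a call is made, the rule gives no failure under either clock, so choosing a clock does not by itself solve the attribution problem. Nor does the cure rule in every case. A subject with an implant who is moved to another drug at week 12 has not exceeded a plan that runs until removal. A subject switched at week 2 who completes a planned 6 weeks on another drug has not exceeded the plan either.

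**4. Size.** Each such subject counted as a success adds 1/50 = 2 percentage points. The number m is not in the documents. Purely as an illustration, assume that m of the 50 are symptom-free after a switch and that 80% of the other 50 − m succeed (the protocol's anticipated cure rate, borrowed here).

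| m (assumed) | Not counted as successes: 0.8(50 − m)/50 | Counted as successes: [0.8(50 − m) + m]/50 | Gap (m/50) |
|---|---|---|---|
| 2 | 76.8% | 80.8% | 4 points |
| 5 | 72% | 82% | 10 points |
| 10 | 64% | 84% | 20 points |

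For scale, the plan's own interval of 69% to 91% has a half-width of 1.96 × √(0.8 × 0.2/50) = 11.1 points. The gap would reach that at about 11.1/2 ≈ 5.5 subjects.

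**The case against.** There is a fair case that this is only loose wording.

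- Section 9(b) describes the course of antibiotics as 4 to 12 weeks. Read that way, antibiotics in the call timing means the study course, and the calls of subjects who complete it fit the range. This reading is possible, but it leaves the other drug unaccounted for at the call.
- A reader might infer that every switched subject misses the call window and so drops out of long-term efficacy. The documents do not support that. The 16 to 24 weeks describe length of participation, not an analysis window, and nothing voids a later call. Section 9(c) ties analyzability to follow-up through week 12, not to the call. Only subjects with more than about 12 weeks of antibiotics in total fall outside.
- Because 9(c) enrolls until 50 subjects have completed follow-up to week 12, subjects who withdraw early are replaced and are largely not among the 50. That narrows the affected group towards subjects who continue beyond week 12.
- The cure rule in 9(f) already catches unplanned extra antibiotics and unplanned surgery, and 9(g) has both treatment duration and unplanned surgery recorded at visits. This stands for those subjects up to the last visit. It does not cover a switch within the planned course, or events between the last visit and the call.
- The body of the protocol lists well-being, recurrence, and self-reported conditions or adverse events as call topics, with record review as needed. The full data fields are in an attachment not available here. One can say that the body lists no question on antibiotics or surgery, but not that the survey omits them.

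**Conclusion.** The point holds as a gap in the definition of long-term efficacy. The start of the three months is undefined once another antibiotic follows tedizolid, the stated range is not reconciled with the sections that foresee longer or replacement therapy, and the recurrence-only rule lets a subject who is symptom-free on or after another Gram-positive drug count as a tedizolid success. Any such misclassification pushes the rate upward by 2 points per subject among 50.

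The total is unknown. The 4, 10 and 20 point gaps rest on assumed counts and on a borrowed 80%, and should not be read as estimates of bias in this trial. Efficacy is a tertiary endpoint of a descriptive, non-comparative pilot, and the primary tolerability result is untouched, so the priority is low to moderate.

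**What to change.** 1. State one start date for the three months and use it in 9(e), 9(f), 9(g) and 9(k). Reconcile the 16 to 24 weeks with the provisions in 9(g) and 9(l). The range needs rewording under either clock: counting from the last tedizolid dose, a subject who stops at week 2 is called at week 14; counting from the last antibiotic, calls can fall after week 24. The choice is a trade-off, since the first clock can give an assessment made under another drug and the second can give a late one. State also that switched subjects, and withdrawn subjects who agree, are called.
2. If the attached survey does not already have them, add dated questions: any antibiotic for the index infection since the last tedizolid dose, whether it is still being taken, and any further surgery at the site.
3. Count unplanned further antibiotics or unplanned surgery for the index infection as long-term failure, in line with the cure rule in 9(f).
4. Report subjects who moved to another Gram-positive antibiotic within their planned course, or who are still on one at the call, as a separate category and not as tedizolid successes. Leave out co-administered antibiotics for other organisms, which 9(b) permits. Give the long-term rate with these subjects in the denominator. A blanket rule that any later antibiotic is failure would conflict with the implant provision in 9(f) and with 9(b), so it is not suggested.

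The cost is a few sentences, up to three survey questions, and a call to some subjects who might otherwise not have had one. Treatment does not change. The downside is that the reported long-term success rate may be lower.

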No materials will be used to directly recruit patients. Flyers will be given to select Inpatient and Outpatient Clinic staff. Flyers will also be given to physicians outside Harbor UCLA Medical Center. Once the physician identifies a potential patient and receives verbal consent from the patient, the physician will call the study staff. At that point the study staff will screen the patient via phone and a waiver of written consent will be utilized for screening purposes only.

Describe the amount and timing of any payments to subjects.

The subjects will be paid in cash for their follow up visits. They will be paid \$30 for the visit on week 1, \$35 for the visit on week 2, \$40 for the visit on week 3, \$40 for the visit on week 4, \$45 for the visit on week 5, \$45 for the visit on week 6, and \$50 each visit for visits on weeks 7, 8, 9, 10, 11, 12 and 13.

The total amount of compensation will range between \$240 and \$585 based on the number of follow up visits the subject completes. All subjects will complete visits on Weeks 1,2,3,4,5, and 12. Subjects still taking the study drug at week 6 will be required to return for a Week 6 follow up visit. Subjects still taking the study drug at week 7 will be required to return for a week 7 follow up visit, and so on- while patients are receiving the study drug they will return for weekly follow up visits until they have completed the course, or until they have reached 12 weeks. Once subjects complete the course of the study drug, they will return for one additional weekly follow up visit (e.g. if a patient completes the study drug at 7 weeks, they will return for visits on weeks 1-8 and week 12). If subjects take the study drug for 12 weeks, they will return for a final follow up visit on week 13.

b) Inclusion and Exclusion Criteria*

Describe how you will screen for eligibility.

Describe the criteria that define who will be included or excluded in your final study sample.

For this investigation, we will use strict inclusion and exclusion criteria.

Inclusion criteria will include:

a) Treatment of bone and joint infection in which therapy for Gram-positive organisms is suspected or documented, as determined by the treating physician and treatment of at least 4 weeks is planned. Bone and joint infection and trauma-associated bone and joint infection will

PROTOCOL TITLE: *Tolerability, Safety, and Efficacy of Tedizolid as Oral Treatment for Bone and Joint Infection*

Revised: 8/10/18 Version 1.6

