Once informed consent is obtained, we will collect data on all subjects' demographics, co-morbidities, surgical history, pertinent microbiology results, and all concomitant medications using standardized forms. For exclusion criteria e) and f) regarding cytopenias and liver function, CBC/CMPs from the past 14 days will be evaluated through a medical chart review. Note that if a CBC has not been performed within the past 14 days, a CBC will be performed on the day of enrollment prior to any study drug being administered to ensure the patient does not meet exclusion criteria (see exclusion criteria e) and f)).

Upon confirmation of eligibility, the study coordinators will call the pharmacy, which will be the LA BioMed Investigational Drug Service (IDS). The research pharmacists at the LABioMed Investigational Drug Service (IDS) will dispense the medication to the subject. Subjects will be given detailed verbal instructions on the use of the medication in either English or Spanish as preferred by the subject. The subject will be given a medication diary and asked to record the time of day when they take each pill as well as any side effects or comments. The subject will be given a small card to keep on their person with information about the study and study staff and emergency contact information. The study staff will answer any questions that the subject has at this time and will encourage the subject to contact the study staff with any future questions.

The subject will present to the Clinical and Translational Research Unit (CTR), the clinical site of the UCLA Clinical and Translational Science Institute (CTSI) on the Harbor-UCLA campus for follow up visits. These follow up visits will occur at week 1, week 2, week 3, week 4, week 5, week 6, week 7, week 8, week 9, week 10, week 11, week 12 and week 13. All subjects will return for follow up visits on weeks 1 – 5 and 12, and subjects still taking the study drug after week 5 will continue to return for weekly follow up visits until they complete the course or until they reach 12 weeks. Once subjects complete the course of the study drug, they will return for one additional weekly follow up visit (e.g. if a patient completes the study drug at 7 weeks, they will return for visits on weeks 1-8 and week 12). If subjects take the study drug for 12 weeks, they will return for a final follow up visit on week 13.

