At each follow up visit, CBC and CMP (comprehensive chemistry panel including liver function tests) will be collected via a blood draw. This blood sample will be sent to Quest Diagnostics by the

PROTOCOL TITLE: *Tolerability, Safety, and Efficacy of Tedizolid as Oral Treatment for Bone and Joint Infection*

Revised: 8/10/18 Version 1.6

CTSI/CTRU, an outside laboratory that is contracted with the CTSI/CTRU to process blood samples. Additionally, standardized surveys (See Data Collection Fields V 1.0, Neuropathy Scale V 1.0, attached) will be administered about drug side effects and tolerability, and adverse events will be measured using the Medical Dictionary for Regulatory Activities Terminology (MedDRA) version 18.1 (or the most current version). At these follow up visits, we will also record data points relevant to defining the efficacy of the treatment, such as the duration of the antibiotic treatment, any unplanned surgical procedures prompted by inadequate infection control, recurrence of signs or symptoms of bone and joint infection, and any other relevant comments or observations from the subject. The subject will also be asked to bring their study drug medication bottle and medication diary in order to assess compliance. If a subject suspects pregnancy during a follow up visit, they will be given a pregnancy test and the study team will track their reported menstrual cycle. If the subject does become pregnant, they will be discontinued from the study drug. Study staff will follow and collect data on the course of the pregnancy and the health of the child for at least 6-8 weeks after delivery.

Patients with evidence of myelosuppression will continue to have weekly CBCs performed until resolution of the myelosuppression.

Subjects who are concurrently taking serotonergic agents while receiving the study drug will be monitored for signs and symptoms of serotonin syndrome at each scheduled follow-up visit. Symptoms of serotonin syndrome include agitation or restlessness, confusion, rapid heartbeat and high blood pressure, dilated (big) pupils, loss of muscle coordination or twitching muscles, muscle rigidity (stiffness), heavy sweating, diarrhea, headache, shivering and goose bumps.

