The study is descriptive and thus no formal statistical analysis plan has been performed. The number of subjects chosen (n=50) is based on a sample size believed to have sufficient power to reassure clinicians that tedizolid is safe, tolerable, and efficacious for the treatment of native bone and hardware-associated bone and joint infection.

Of note, confidence intervals for safety and efficacy will be calculated. Confidence intervals for outcomes of low incidence (e.g., thrombocytopenia) will be approximately +/-3 - 7%. E.g., assuming n=50 subjects, a low incidence outcome with a probability of 2.5% will have 95% confidence intervals of <0.1%-6.8%. Outcomes with probabilities farther from 0% or 100% will have wider confidence intervals. For example, we anticipate cure rate will be 80%, in which assuming n=50, 95% confidence intervals will be 69%-91%.

Provide a power analysis.

Confidence intervals for safety and efficacy will be calculated. Confidence intervals for outcomes of low incidence (e.g., thrombocytopenia) will be approximately +/-3 - 7%. E.g., assuming n=50 subjects, a low incidence outcome with a probability of 2.5% will have 95% confidence intervals of <0.1%-6.8%. Outcomes with probabilities farther from 0% or 100% will have wider confidence intervals. For example, we anticipate cure rate will be 80%, in which assuming n=50, 95% confidence intervals will be 69%-91%.

Describe the steps that will be taken to secure the data (e.g., training, authorization of access, password protection, encryption, physical controls, certificates of confidentiality, and separation of identifiers and data) during storage, use, and transmission.

All source documents and specimens will be coded meaning these items will be labeled the subjects Study ID number and will include dates (case report forms) rather than his/her name and/or date of birth. We will maintain a separate password-protected key list/log (electronic file) linking each subject to their Study ID and a hardcopy will be maintained separate from individual subject files in a separate locked filing cabinet. Access to study computers and files will be limited to study personnel. Human research records including Informed Consent Forms

PROTOCOL TITLE: *Tolerability, Safety, and Efficacy of Tedizolid as Oral Treatment for Bone and Joint Infection*

Revised: 8/10/18 Version 1.6

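### Stopping or interrupting tedizolid for side effects is not part of the primary tolerability endpoint, and subjects who stop can fall outside the 50 completers on whom the intervals rest

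*Combined protocol and SAP*

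**What the plan says.** Section 9 f), Study Endpoints, gives the primary endpoint: "The primary study endpoint is the tolerability of prolonged (≥ 4 weeks) courses of tedizolid antibiotic therapy". The secondary endpoint has the same form: "The secondary study endpoint is the safety of prolonged (≥ 4 weeks) courses of tedizolid antibiotic therapy". The measures named for both are CBC and chemistry panels, adverse events coded in MedDRA, and surveys; for the primary endpoint, "We will administer standardized surveys about drug side effects and tolerability at all follow-up visits". There is no rule for when a subject has tolerated a course, and no mention of doses taken, interruptions or discontinuation.

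Entry depends on intention. Under inclusion criterion a) in section 9 b), "treatment of at least 4 weeks is planned".

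Dose-taking is recorded. Section 9 g) says subjects receive a diary and are "asked to record the time of day when they take each pill as well as any side effects or comments". At follow-up visits they are "asked to bring their study drug medication bottle and medication diary in order to assess compliance". No compliance measure or analysis follows. The diary is not wholly unused: section 9 k) makes it a source of safety information that staff review.

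Section 9 c) sets the target as 50 analyzable subjects with every follow-up through week 12 completed, and expects about 55 to be enrolled for 10% attrition. Section 9 l) allows withdrawal for, among other things, gastrointestinal intolerance, cytopenias or neuropathy symptoms, and asks for no further visits after withdrawal. Section 9 i) describes the study as descriptive, without a formal statistical analysis plan. It says that "confidence intervals for safety and efficacy will be calculated" and works its examples at n=50.

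**The concern.** Having to stop or pause a drug because of its side effects is the most direct evidence that it is not tolerated. A primary tolerability endpoint that does not count this misses the outcome a clinician would ask about first.

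The choice of subjects adds to the problem. If the rates are computed on those who completed all follow-up to week 12, and those who withdraw are replaced as attrition, then membership of the analysed group can depend on the outcome being measured. The resulting error favours the drug. The trial is open-label with no comparator, so no control arm would reveal it. Section 9 i) says the sample size was chosen to reassure clinicians that the drug is safe and tolerable, so the direction of the error matters.

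Exposure matters as well. Section 10 reports a possible dose and duration effect on blood counts beyond 6 days, and neuropathy with another drug of the class after more than 28 days. Toxicity rates for courses of 4 weeks or more are hard to interpret without the number of doses actually taken.

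**Working it through.** **1. The plan's own figures.** Inputs from sections 9 c) and 9 i): n=50, rates of 2.5% and 80%, attrition 10%. Formula: p ± 1.96·√(p(1−p)/n).

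- p=0.025: half-width 1.96·√(0.025·0.975/50) = 0.043, giving −1.8% to 6.8%. The plan prints <0.1% to 6.8%.
- p=0.80: half-width 1.96·√(0.8·0.2/50) = 0.111, giving 68.9% to 91.1%. The plan prints 69% to 91%.
- Enrolment: 50/(1−0.10) = 55.6. The plan says approximately 55.

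The figures reproduce. All use 50 as the denominator, and none depends on adherence or on why subjects left.

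**2. How a subject who stops for intolerance can leave the denominator.**

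- Section 9 l): gastrointestinal intolerance is a permitted reason for withdrawal.
- Section 9 l): after withdrawal no further visits are required.
- Section 9 c): a subject without all follow-up through week 12 does not count towards the 50, and enrolment continues until 50 do.
- Section 9 i): the precision figures are for those 50.

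The documents do not define analyzable and do not say that withdrawn subjects will be left out of the tolerability rates. They leave that open.

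**3. Possible size through the denominator.** Assume 55 subjects take at least one dose, 50 complete, and 45 of the 50 appear to have tolerated treatment (an illustrative value). The five who left may have done so for any reason.

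| Of the 5 who left, stopped for intolerance | Tolerated, all dosed | Rate |
|---|---|---|
| Completers only | 45/50 | 90.0% |
| 0 | 50/55 | 90.9% |
| 3 | 47/55 | 85.5% |
| 5 | 45/55 | 81.8% |

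The exact (Clopper-Pearson) 95% interval is 78.2% to 96.7% for 45/50 and 69.1% to 90.9% for 45/55.

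For the stopping rate itself, the extreme case is 0/50 among completers (exact upper limit 7.1%) against 5/55 among all dosed subjects: 9.1%, exact interval 3.0% to 20.0%.

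**4. Possible size through the numerator.** One subject of 50 is 1/50 = 2 percentage points. If 45/50 seemed to tolerate the drug and 3 or 5 of those had in fact interrupted it because of side effects, the rate becomes 42/50 = 84% or 40/50 = 80%. For scale, the plan's interval method at 90% has half-width 1.96·√(0.9·0.1/50) = 0.083, about 8 points.

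The counts in steps 3 and 4 are assumptions that show sensitivity. The documents give no rate of missed doses or of stopping for side effects.

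**The case against.** The strongest reply is that side effects are already well covered. A subject who skips tablets because of nausea still has nausea. It is asked about in the visit surveys, can be written in the diary, is reviewed by staff and is coded as an adverse event. The study is also a descriptive pilot, and whoever analyses it would probably summarise compliance anyway. Much of this stands. A side effect behind a missed dose will usually be recorded, so failing to define adherence would, by itself, be only missing detail. It does not answer the problem of subjects who withdraw: they need attend no further visits and may not be among the 50.

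A reader might infer that subjects who skip doses are scored as having tolerated a full course. The documents do not say so. They contain no scoring rule, and the plan is silent.

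A reader might also take 4 weeks to mean 28 doses, so that one missed tablet disqualifies a course. The hypotheses speak of courses of at least 4 weeks and name no dose count. Therapy runs from 4 to 12 weeks, so a longer plan could pass such a threshold despite many missed tablets.

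Nor do the documents support a numerical claim that tolerability is overstated by a given amount. Any such figure only returns the proportion of hidden intolerance that was assumed.

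Stopping the drug is also not the same as leaving the study. A subject could stop and still attend through week 12, and so remain in the 50. Finally, the data collection form and diary template are attachments outside the text reviewed, so a field for the reason a dose was missed may already exist. That would ease the fix but would not give the data a role in the analysis.

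**Conclusion.** The point holds in this form. The primary tolerability endpoint does not count stopping or interruption for side effects. The dose-taking data and bottle check have no stated analytic role, although the diary's side-effect entries are reviewed for safety. The completer-based target of 50, with no visits required after withdrawal, lets subjects who stop for intolerance fall outside the group on which the planned intervals rest.

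The error would favour the drug. Its size is unknown. In the illustration, the plan's own 10% attrition bounds the denominator effect: completers show 90%, while the all-dosed rate lies between 81.8% and 90.9% depending on why five subjects left. This assumes that 55 are dosed, that 45 of 50 completers tolerate treatment, and that the rates are in fact computed on completers, which the documents imply but do not state. The protocol says attrition is uncertain, so actual losses could be larger or smaller. Neither biased reporting nor poor adherence is demonstrated. The gap should be closed before analysis because, without a rule, the handling of these subjects could be chosen after the data are seen.

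**What to change.** In sections 9 f) and 9 i):

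1. Add, as a component of the primary endpoint, the proportion of all subjects who took at least one dose who stopped or interrupted tedizolid because of a side effect, with its 95% interval. An exact interval suits small counts.
2. Replace the completer set with all dosed subjects for tolerability and safety rates. Recruitment may still aim for 50 completers, but that number should not be the denominator.
3. Summarise doses actually taken, from the diary and bottle check, alongside these rates. Any table by exposure should be supportive only and should take account of planned duration, since longer plans accumulate more doses regardless of adherence.
4. Record the reason for each interruption or stop at the visit or at withdrawal, if the existing form does not already do so.

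The cost is analysis wording, perhaps one data field and one table. No visits or tests are added. The tolerability figure may be less favourable, and the diary is partly self-report, so the dose summary will be approximate.
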